# Iteration for tabling and graphing FOR ITT ----
if(dir.exists("itt"))
  unlink("itt",recursive = T,force=T)
dir.create("itt")
setwd("itt/")
for(i in 1:2){ # For NIHSS and WAB raw scores only graph them
  dfl<-db_long[,c("RDMNUM","is_crb","visit",db_names$short[i])]
  g<-graph_them_all(dfl,db_names$long[i],paste0(i," ",db_names$long[i]))
  png(paste0(i,db_names$short[i],".png"),width = 800,height = 600)
  print(g)
  dev.off()
}
for(i in 1:2+2){ # For NIHSS and WAB differentials graph them and do tables
  dfl<-db_long[db_long$visit!=1,c("RDMNUM","is_crb","visit",db_names$short[i])]
  g<-graph_them_all(dfl,db_names$long[i],paste0(i," ",db_names$long[i]))
  t<-table_them_all(dfl,already_diff = T)
  png(paste0(i,db_names$short[i],".png"),width = 800,height = 600)
  print(g)
  dev.off()
  write.xlsx(t,paste0(i,db_names$short[i],".xlsx"))
}
for(i in 5:6){ # For mRS and BI graph and make tables, but with already_diff=F
  dfl<-db_long[db_long$visit!=1,c("RDMNUM","is_crb","visit",db_names$short[i])]
  g<-graph_them_all(dfl,db_names$long[i],paste0(i," ",db_names$long[i]))
  t<-table_them_all(dfl,already_diff = F)
  png(paste0(i,db_names$short[i],".png"),width = 800,height = 600)
  print(g)
  dev.off()
  write.xlsx(t,paste0(i,db_names$short[i],".xlsx"))
}

```

```
setwd("../")
# Iteration for tabling and graphing FOR PP ----
db_long<-db_long[db_long$is_pp,]
if(dir.exists("pp"))
  unlink("pp",recursive = T,force=T)
dir.create("pp")
setwd("pp/")
for(i in 1:2){ # For NIHSS and WAB raw scores only graph them
  dfl<-db_long[,c("RDMNUM","is_crb","visit",db_names$short[i])]
  g<-graph_them_all(dfl,db_names$long[i],paste0(i," ",db_names$long[i]))
  png(paste0(i,db_names$short[i],".png"),width = 800,height = 600)
  print(g)
  dev.off()
}
for(i in 1:2+2){ # For NIHSS and WAB differentials graph them and do tables
  dfl<-db_long[db_long$visit!=1,c("RDMNUM","is_crb","visit",db_names$short[i])]
  g<-graph_them_all(dfl,db_names$long[i],paste0(i," ",db_names$long[i]))
  t<-table_them_all(dfl,already_diff = T)
  png(paste0(i,db_names$short[i],".png"),width = 800,height = 600)
  print(g)
  dev.off()
  write.xlsx(t,paste0(i,db_names$short[i],".xlsx"))
}
for(i in 5:6){ # For mRS and BI graph and make tables, but with already_diff=F
  dfl<-db_long[db_long$visit!=1,c("RDMNUM","is_crb","visit",db_names$short[i])]
  g<-graph_them_all(dfl,db_names$long[i],paste0(i," ",db_names$long[i]))
  t<-table_them_all(dfl,already_diff = F)
  png(paste0(i,db_names$short[i],".png"),width = 800,height = 600)
  print(g)
  dev.off()
  write.xlsx(t,paste0(i,db_names$short[i],".xlsx"))
}
setwd("../")
# AE preprocessing ----
# NB: if the AE classification is not complete, i.e. there are still NAs, fill them with the following
command (pay attention to which columns you execute this on)
for(i in 11:22) db_advers[is.na(db_advers[,i]),i]<-0
# NB: if the SAE classification is not complete, ditto
db_advers[is.na(db_advers[,3]),3]<-"no"

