## Safety analysis in safety population

The Safety Population (SP) includes all trial participants who were registered in the trial and received at least one dose of treatment, irrespective of their subsequent adherence to the protocol or premature discontinuation. Unlike ITT, SP analysis focuses on AEs and SAEs caused by the treatment, thus evaluating the safety-related parameters of the products. Patients are included in this population irrespective of missing data or premature discontinuation.

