# Load data - this might change ----
db_scores<-data.frame(read_excel("dbfin.xlsx","only_total_scores"))
db_bigdat<-data.frame(read_excel("dbfin.xlsx","escas_data"))
db_assign<-data.frame(read_excel("rndtest.xlsx"))

```

```

db_advers<-data.frame(read_excel("dbfin.xlsx","adverse_events"))
names(db_assign)<-c("RDMNUM","is_crb","is_pp")

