# AE information table -----
db_adver2<-db_assign
for(i in 1:nrow(db_adver2)){
  rdmnum<-db_adver2$RDMNUM[i]
  db_adver2[i,"AE_total"]<-sum(db_advers$RDMNUM==rdmnum)
```

```
db_adver2[i,"SAE_total"]<-sum(db_advers$RDMNUM==rdmnum&db_advers$SAE=="yes")
for(j in
c("neurological","psychiatric","cardiovascular","renal","hematological","gastrointestinal","metabol
ic","respiratory","immune.related.AE","ENT","ophthalmic","osteoarticular"))
  db_adver2[i,paste0("AE_",j)]<-
sum(db_advers$RDMNUM==rdmnum&db_advers[,paste0("is_",j)]==1)
}
tbl_out<-data.frame(
  AE_category=as.character(),
  sub=as.character(),
  Crb=as.character(),
  Plc=as.character(),
  pval=as.character(),
  test=as.character()
)
db_aelong<-data.frame(
  AE_category=as.character(),
  is_crb=as.logical(),
  no_patients=as.numeric(),
  no_aes=as.numeric(),
  percent_patients=as.numeric()
)
for(i in 7:20){
  rws<-nrow(tbl_out)
  tbl_out[rws+1,1]<-db_names[i,"short"]
  tbl_out[rws+1:5,2]<-c("Patients with AEs in group","Total number of AEs in group","Mean
number of AEs per patient","Median (Q1-Q3) number of AEs per patient","Max number of AEs
per patient")
  xc<-db_adver2[db_adver2$is_crb,db_names[i,"short"]]
  xp<-db_adver2[!db_adver2$is_crb,db_names[i,"short"]]
  tbl_out[rws+1,3]<-paste0(sum(xc!=0)," (",round(sum(xc!=0)/length(xc)*100,3),"%)")
  tbl_out[rws+1,4]<-paste0(sum(xp!=0)," (",round(sum(xp!=0)/length(xp)*100,3),"%)")
  x<-contingency.table.test(table(db_adver2$is_crb,db_adver2[,db_names[i,"short"]]!=0))
  tbl_out[rws+1,5]<-beautiful.p.value(x[["p_chosen"]])
  tbl_out[rws+1,6]<-x[["shorthand"]]
  tbl_out[rws+2,3]<-sum(xc)
  tbl_out[rws+2,4]<-sum(xp)
  tbl_out[rws+3,3]<-descr.numeric.meansd(xc)
  tbl_out[rws+3,4]<-descr.numeric.meansd(xp)
  tbl_out[rws+4,3]<-descr.numeric.median(xc)
  tbl_out[rws+4,4]<-descr.numeric.median(xp)
  tbl_out[rws+5,3]<-max(xc)
  tbl_out[rws+5,4]<-max(xp)
  x<-test.numeric.unpaired(xc,xp)
```

```

tbl_out[rws+3,5]<-beautiful.p.value(x$p.value)
tbl_out[rws+3,6]<-x$final.test
for(j in 1:max(xc, xp)){
  tbl_out[rws+5+j,2]<-paste0("Patient with ",j," AEs")
  tbl_out[rws+5+j,3]<-paste0(sum(xc==j)," (",round(sum(xc==j)/length(xc)*100,3),"%)")
  tbl_out[rws+5+j,4]<-paste0(sum(xp==j)," (",round(sum(xp==j)/length(xp)*100,3),"%)")
}
rws<-(i-7)*2
db_aelong[rws+1:2,1]<-db_names[i,"short"]
db_aelong[rws+1:2,2]<-c(T,F)
db_aelong[rws+1,3]<-sum(xc!=0)
db_aelong[rws+2,3]<-sum(xp!=0)
db_aelong[rws+1,4]<-sum(xc)
db_aelong[rws+2,4]<-sum(xp)

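### The safety code recodes missing seriousness to not serious and tabulates all assigned patients, both against the SAP text, so SAE figures can be understated and the Safety Population is not what gets analysed

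*SAP*

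**What the plan says.** **Seriousness.** Under AE preprocessing in the supplementary R code, the comment "NB: if the SAE classification is not complete, ditto" introduces the command "db_advers[is.na(db_advers[,3]),3]<-'no". The comment is conditional but the command is not: it acts on whatever is missing and keeps no record of how many events it changed. SAEs are then counted per patient by "sum(db_advers$RDMNUM==rdmnum&db_advers$SAE=='yes", so only events marked yes contribute. Total AEs are counted by "sum(db_advers$RDMNUM==rdmnum", which ignores seriousness.

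**AE classes.** A parallel line, "for(i in 11:22) db_advers[is.na(db_advers[,i]),i]<-0", sets missing class flags to zero.

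**Missing data.** The Missing data handling section says the plan does without imputation and relies on listwise deletion (PP) or pairwise deletion (ITT). No text section mentions the two fills.

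**Population.** The Safety Population, under Safety analysis in safety population, "includes all trial participants who were registered in the trial and received at least one dose of treatment". The code for the AE information table starts from "db_adver2<-db_assign", and its percentages divide by the number of assigned patients in each arm. The assignment file has three fields, set by "names(db_assign)<-c('RDMNUM','is_crb','is_pp". None of them records dosing, and the list of database columns under Coding systems utilized has no dosing variable either.

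**The concern.** SAE incidence is a named secondary outcome. A value left blank because classification is unfinished means not yet assessed, which is different from known to be non-serious. Filling it with no is single-value imputation, and its only possible error is towards too few SAEs. A reader of the safety table would not see that it had happened.

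The population problem is separate. As written, the code's safety set is the ITT set, so the Safety Population defined in the text cannot be produced by the program meant to analyse it. If any randomised patient never received treatment, the published denominators will not match the definition.

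**Working it through.** The SAP gives no SAE count, AE rate, number of missing seriousness values or number of undosed patients, so there is no figure of its own to reproduce. The logic below comes from the code. The counts are assumptions, with 60 per arm taken from the SAP's sample size section.

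**1. Direction of the seriousness fill.** SAE total per patient = number of that patient's events marked yes.
- If a missing value is truly no, the fill is correct.
- If it is truly yes, the SAE count falls by one.
- The number of patients with an SAE falls only if that event was the patient's sole SAE.
- The AE total counts all rows and is unchanged.

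The error is therefore zero or downward.

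**2. Possible size.** If 6/60 = 10.0% of an arm is coded as having an SAE, the worst case is:
- 7/60 = 11.7% with one further patient whose only possible SAE is unclassified;
- 9/60 = 15.0% with three.

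If the gaps sit in one arm only, 3/60 versus 3/60 (5.0% each) as coded could be 8/60 versus 3/60 (13.3% versus 5.0%) with five such patients.

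**3. Effect on the planned test.** The code uses the uncorrected chi-square test if all expected counts are at least 5, and Fisher's exact test otherwise. The SAP's threshold is two-sided 0.05.

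| Assumed patients with SAE | Smallest expected count | Test chosen | p |
|---|---|---|---|
| 8/60 vs 2/60 (true) | 60×10/120 = 5.0 | Chi-square | 0.048 |
| 5/60 vs 2/60 (three filled as no) | 60×7/120 = 3.5 | Fisher | 0.44 |

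For the first row, chi-square = 120×(8×58 − 2×52)² / (60×60×10×110) = 15,552,000/3,960,000 = 3.93, so p = 0.048. The difference in rates drops from 10.0 to 5.0 percentage points.

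**4. Denominator.** Suppose u of 60 patients in an arm were never dosed and have no recorded AE. Then reported rate = rate among dosed × (60 − u)/60.

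| u | Factor | A 30% rate becomes |
|---|---|---|
| 0 | 1.000 | 30.0% |
| 1 | 0.983 | 29.5% |
| 3 | 0.950 | 28.5% |
| 6 | 0.900 | 27.0% |

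Each such patient costs 1/60, or about 1.7%, in relative terms. The direction reverses if the undosed patient has a recorded AE: 18/59 = 30.5% among dosed patients becomes 19/60 = 31.7% among assigned patients.

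**5. What happens if the fill is simply deleted.** A small test data set run through the counting logic shows that one unclassified event makes the SAE count and percentage of its arm missing. Removing the line is therefore not enough; the values must be resolved or handled by an explicit rule.

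**The case against.** The strongest reply is that both problems may be empty in practice. The comments present the fills as contingencies. The Data eligibility section requires inspection of the data, with abnormalities preferably settled before unblinding. The Randomisation section has the analysis populations determined before unblinding. The assignment file is described as a test file, and the loading code is expected to change. The Source code section requires later changes to be documented and the final code released. The trial is exploratory, with no confirmatory analysis, and safety is secondary. One may also say that the remark on imputation was meant for efficacy scores, since listwise and pairwise deletion are assigned only to PP and ITT.

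Much of this stands as a limit on likelihood and weight. It does not remove the contradiction. None of these provisions guarantees complete seriousness data or names a dosing filter, and the same Source code section says the code should ideally stay unchanged after unblinding. If the imputation remark covers efficacy only, the SAP text has no rule at all for missing seriousness. The statement that safety patients are kept irrespective of missing data concerns who is included; it does not say how an event is classified.

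Two stronger readings are tempting, and the documents support neither:
- **That SAEs and safety rates are understated.** This would need unclassified events that were serious, or undosed patients without events. The SAP reports neither. More missing values in one arm than the other is also speculation in a double-blind trial.
- **That the class-flag fill hides events.** The Coding systems section says only some AEs are classified further, so a blank may properly mean not in this class, and the event still counts in the AE total. The code's own comment, however, also covers unfinished classification, and the code cannot tell the two apart. A check is enough there.

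**Conclusion.** The safety code departs from the SAP text in two places. The seriousness fill can understate SAE counts and incidence and can never overstate them; total AEs are unaffected. The safety table uses all assigned patients instead of those dosed. That shifts rates by about 1.7% in relative terms per undosed, event-free patient in an arm of 60. The shift is zero if all were dosed, and may be upward if an undosed patient has a recorded AE.

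The illustration, in which p moves from 0.048 to 0.44, assumes that three of eight SAE patients in one arm have missing seriousness and none in the other. It shows what a few fills can do and is not a forecast. The actual size cannot be known from the document. The point should be fixed, because the remedy is specific and cheap. It is not grounds for doubting the trial as a whole.

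**What to change.** 1. Add a Safety Population flag (at least one dose received) to `db_assign`, and subset `db_adver2` to it before any counting, so that table and graph denominators follow the SAP definition.
2. Replace the seriousness fill with a check that stops the program if any value is missing. Query seriousness to completion before database lock.
3. Where a value cannot be obtained, let the program pass that check only through a documented list. Report the number of unclassified events by arm, and add a sensitivity table that counts them as serious. Counting them as serious in the main table would swap one single-value imputation for its opposite.
4. For the class flags, confirm before lock that a blank means not in this class and does not mean not yet classified.
5. State these rules in the Missing data handling section so that text and code agree.

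The cost is a few lines of code, one extra flag, and a query round on AE records already held. Design and sample size do not change.

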# AE information table -----
db_adver2<-db_assign
for(i in 1:nrow(db_adver2)){
  rdmnum<-db_adver2$RDMNUM[i]
  db_adver2[i,"AE_total"]<-sum(db_advers$RDMNUM==rdmnum)
```

```
db_adver2[i,"SAE_total"]<-sum(db_advers$RDMNUM==rdmnum&db_advers$SAE=="yes")
for(j in
c("neurological","psychiatric","cardiovascular","renal","hematological","gastrointestinal","metabol
ic","respiratory","immune.related.AE","ENT","ophthalmic","osteoarticular"))
  db_adver2[i,paste0("AE_",j)]<-
sum(db_advers$RDMNUM==rdmnum&db_advers[,paste0("is_",j)]==1)
}
tbl_out<-data.frame(
  AE_category=as.character(),
  sub=as.character(),
  Crb=as.character(),
  Plc=as.character(),
  pval=as.character(),
  test=as.character()
)
db_aelong<-data.frame(
  AE_category=as.character(),
  is_crb=as.logical(),
  no_patients=as.numeric(),
  no_aes=as.numeric(),
  percent_patients=as.numeric()
)
for(i in 7:20){
  rws<-nrow(tbl_out)
  tbl_out[rws+1,1]<-db_names[i,"short"]
  tbl_out[rws+1:5,2]<-c("Patients with AEs in group","Total number of AEs in group","Mean
number of AEs per patient","Median (Q1-Q3) number of AEs per patient","Max number of AEs
per patient")
  xc<-db_adver2[db_adver2$is_crb,db_names[i,"short"]]
  xp<-db_adver2[!db_adver2$is_crb,db_names[i,"short"]]
  tbl_out[rws+1,3]<-paste0(sum(xc!=0)," (",round(sum(xc!=0)/length(xc)*100,3),"%)")
  tbl_out[rws+1,4]<-paste0(sum(xp!=0)," (",round(sum(xp!=0)/length(xp)*100,3),"%)")
  x<-contingency.table.test(table(db_adver2$is_crb,db_adver2[,db_names[i,"short"]]!=0))
  tbl_out[rws+1,5]<-beautiful.p.value(x[["p_chosen"]])
  tbl_out[rws+1,6]<-x[["shorthand"]]
  tbl_out[rws+2,3]<-sum(xc)
  tbl_out[rws+2,4]<-sum(xp)
  tbl_out[rws+3,3]<-descr.numeric.meansd(xc)
  tbl_out[rws+3,4]<-descr.numeric.meansd(xp)
  tbl_out[rws+4,3]<-descr.numeric.median(xc)
  tbl_out[rws+4,4]<-descr.numeric.median(xp)
  tbl_out[rws+5,3]<-max(xc)
  tbl_out[rws+5,4]<-max(xp)
  x<-test.numeric.unpaired(xc,xp)
```

```

tbl_out[rws+3,5]<-beautiful.p.value(x$p.value)
tbl_out[rws+3,6]<-x$final.test
for(j in 1:max(xc, xp)){
  tbl_out[rws+5+j,2]<-paste0("Patient with ",j," AEs")
  tbl_out[rws+5+j,3]<-paste0(sum(xc==j)," (",round(sum(xc==j)/length(xc)*100,3),"%)")
  tbl_out[rws+5+j,4]<-paste0(sum(xp==j)," (",round(sum(xp==j)/length(xp)*100,3),"%)")
}
rws<-(i-7)*2
db_aelong[rws+1:2,1]<-db_names[i,"short"]
db_aelong[rws+1:2,2]<-c(T,F)
db_aelong[rws+1,3]<-sum(xc!=0)
db_aelong[rws+2,3]<-sum(xp!=0)
db_aelong[rws+1,4]<-sum(xc)
db_aelong[rws+2,4]<-sum(xp)
db_aelong[rws+1,5]<-sum(xc!=0)/length(xc)*100
db_aelong[rws+2,5]<-sum(xp!=0)/length(xp)*100
}
for(i in 1:nrow(tbl_out))
  for(j in 1:ncol(tbl_out))
    if(is.na(tbl_out[i,j])) tbl_out[i,j]<-""
write.xlsx(tbl_out,"AE_table.xlsx")
db_aelong$AE_category2<-factor(rep(1:14,each=2),levels=1:14,labels=c(
  "AE\nall types",
  "SAE",
  "Neurol.", "Psych.", "CV", "Renal",
  "Hematol.", "GI", "Metab.", "Resp.",
  "Immune\nrelated", "ENT", "Ophthalmic", "Osteo-\narticular"
))
db_aelong$fill<-factor(db_aelong$sis_crb,levels=c(F,T),labels=c(
  paste0("Placebo\n(N=",sum(!db_adver2$sis_crb),")"),
  paste0("Cerebrolysin\n(N=",sum(db_adver2$sis_crb),")")
))
g<-ggplot(db_aelong,aes(x=AE_category2,y=no_patients,fill=fill))+
  geom_col(position="dodge")+
  scale_fill_manual(values=c("#6495ED","#ee82ee"))+
  labs(x="AE category",y="Number of patients",fill="Treatment")+
  theme_light()+
  theme(plot.title=element_text(hjust=0),plot.subtitle = element_text(hjust=0),text =
  element_text(size = 25))
png("AE_number_of_patients.png",width=2000,height = 600)
print(g)
dev.off()
g<-ggplot(db_aelong,aes(x=AE_category2,y=no_aes,fill=fill))+
  geom_col(position="dodge")+

```

```
scale_fill_manual(values=c("#6495ED", "#ee82ee"))+
labs(x="AE category", y="Number of AEs", fill="Treatment")+
theme_light()+
theme(plot.title=element_text(hjust=0), plot.subtitle = element_text(hjust=0), text =
element_text(size = 25))
png("AE_number_of_AEs.png", width=2000, height = 600)
print(g)
dev.off()
g<-ggplot(db_aelong, aes(x=AE_category2, y=percent_patients, fill=fill))+
geom_col(position="dodge")+
scale_fill_manual(values=c("#6495ED", "#ee82ee"))+
labs(x="AE category", y="Percent patients of total (%)", fill="Treatment")+
theme_light()+
theme(plot.title=element_text(hjust=0), plot.subtitle = element_text(hjust=0), text =
element_text(size = 25))
png("AE_percent_of_patients.png", width=2000, height = 600)
print(g)
dev.off()
```
